**Table 10-4 HNVs Equation Coefficients by Sex, Race, and Age**

Parameter	Sex	Race	Age		b 0	b 1	b 2	b 3
			(years)					
HNV FEV1	Male	Caucasian	<20		-0.7453	-0.04106	0.004477	0.00014098
			≥20		0.5536	-0.01303	-0.000172	0.00014098
		African American	<20		-0.7048	-0.05711	0.004316	0.00013194
			≥20		0.3411	-0.02309		0.00013194
		Mexican American	<20		-0.8218	-0.04248	0.004291	0.00015104
			≥20		0.6306	-0.02928		0.00015104
	Female	Caucasian	<18		-0.8710	0.06537		0.00011496
			≥18		0.4333	-0.00361	-0.000194	0.00011496
		African American	<18		-0.9630	0.05799		0.00010846
			≥18		0.3433	-0.01283	-0.000097	0.00010846
		Mexican American	<18		-0.9641	0.06490		0.00012154
			≥18		0.4529	-0.01178	-0.000113	0.00012154
HNV FVC	Male	Caucasian	<20		-0.2584	-0.20415	0.010133	0.00018642
			≥20		-0.1933	0.00064	-0.000269	0.00018642
		African American	<20		-0.4971	-0.15497	0.007701	0.00016643
			≥20		-0.1517	-0.01821		0.00016643
		Mexican American	<20		-0.7571	-0.09520	0.006619	0.00017823
			≥20		0.2376	-0.00891	-0.000182	0.00017823
	Female	Caucasian	<18		-1.2082	0.05916		0.00014815
			≥18		-0.3560	0.01870	-0.000382	0.00014815
		African American	<18		-0.6166	-0.04687	0.003602	0.00013606
			≥18		-0.3039	0.00536	-0.000265	0.00013606
		Mexican American	<18		-1.2507	0.07501		0.00014246
			≥18		0.1210	0.00307	-0.000237	0.00014246
HNV FEF25-75%	Male	Caucasian	<20		-1.0863	0.13939		0.00010345
			≥20		2.7006	-0.04995		0.00010345
		African American	<20		-1.1627	0.12314		0.00010461
			≥20		2.1477	-0.04238		0.00010461
		Mexican American	<20		-1.3592	0.10529		0.00014473
			≥20		1.7503	-0.05018		0.00014473
	Female	Caucasian	<18		-2.5284	0.52490	-0.015309	0.00006982
			≥18		2.3670	-0.01904	-0.000200	0.00006982
		African American	<18		-2.5379	0.43755	-0.012154	0.00008572
			≥18		2.0828	-0.03793		0.00008572
		Mexican American	<18		-2.1825	0.42451	-0.012415	0.00009610
			≥18		1.7456	-0.01195	-0.000291	0.00009610
HNV FEV1/FVC%	Male	Caucasian			88.066	-0.2066		
		African American			89.239	-0.1828		
		Mexican American			90.024	-0.2186		
	Female	Caucasian			90.809	-0.2125		
		African American			91.655	-0.2039		
		Mexican American			92.360	-0.2248		

Source: Reference 1 (Tables 4, 5 and 6)

**Table 10-5 WNVs Equation Coefficients by Sex and Age in White Boys and Girls**

Sex	Age	FEV 1		FVC		FEF 25-75%		FEV 1 /FVC	
		$\alpha$	$\beta$	$\alpha$	$\beta$	$\alpha$	$\beta$	$\alpha$	$\beta$
Male	6	-0.109	2.252	-0.024	2.470			-0.078	-0.248
	7	-0.104	2.270	-0.018	2.489			-0.086	-0.220
	8	-0.089	2.257	0.005	2.443	0.264	1.505	-0.091	-0.199
	9	-0.063	2.197	0.017	2.426	0.308	1.443	-0.086	-0.206
	10	-0.057	2.212	0.030	2.407	0.290	1.557	-0.081	-0.209
	11	-0.093	2.324	0.009	2.468	0.242	1.738	-0.101	-0.147
	12	-0.161	2.512	-0.061	2.649	0.165	1.982	-0.101	-0.133
	13	-0.292	2.843	-0.175	2.924	0.007	2.396	-0.116	-0.085
	14	-0.329	2.983	-0.219	3.060	0.014	2.483	-0.106	-0.087
	15	-0.141	2.709	-0.079	2.859	0.241	2.163	-0.060	-0.155
	16	0.062	2.409	0.104	2.591	0.503	1.764	-0.045	-0.178
17	0.262	2.099	0.253	2.374	0.762	1.368	0.008	-0.272	
Female	6	-0.109	1.949	-0.013	2.007			-0.097	-0.055
	7	-0.144	2.243	-0.062	2.385			-0.084	-0.132
	8	-0.137	2.239	-0.055	2.381	0.247	1.668	-0.079	-0.152
	9	-0.123	2.222	-0.039	2.351	0.254	1.710	-0.084	-0.128
	10	-0.161	2.364	-0.068	2.458	0.195	1.933	-0.092	-0.097
	11	-0.223	2.558	-0.120	2.617	0.161	2.091	-0.102	-0.061
	12	-0.264	2.709	-0.174	2.776	0.185	2.120	-0.090	-0.067
	13	-0.153	2.535	-0.061	2.576	0.294	1.976	-0.093	-0.040
	14	0.046	2.178	0.139	2.208	0.450	1.711	-0.096	-0.026
	15	0.148	2.008	0.210	2.099	0.581	1.486	-0.062	-0.093

Source: Reference 2 (Tables 2 and 3)

**Table 10-6 WNVs Equation Coefficients by Sex and Age in Black Boys and Girls**

Sex	Age	FEV 1		FVC		FEF 25-75%		FEV 1 /FVC	
		$\alpha$	$\beta$	$\alpha$	$\beta$	$\alpha$	$\beta$	$\alpha$	$\beta$
Male	6	-0.166	1.723	-0.088	1.961			-0.091	-0.152
	7	-0.122	1.846	-0.040	2.040			-0.091	-0.153
	8	-0.225	2.271	-0.094	2.323	0.097	1.544	-0.118	-0.104
	9	-0.142	2.059	-0.074	2.308	0.255	1.248	-0.079	-0.218
	10	-0.157	2.117	-0.110	2.417	0.230	1.428	-0.047	-0.303
	11	-0.176	2.166	-0.138	2.453	0.256	1.438	-0.048	-0.263
	12	-0.307	2.548	-0.224	2.710	0.085	1.936	-0.084	-0.162
	13	-0.486	2.962	-0.342	2.975	-0.121	2.476	-0.141	-0.018
	14	-0.472	3.010	-0.337	3.035	-0.115	2.536	-0.123	-0.050
	15	-0.318	2.789	-0.226	2.889	0.170	2.120	-0.070	-0.140
	16	0.074	2.140	0.058	2.425	0.663	1.299	0.018	-0.289
17	0.053	2.223	0.148	2.310	0.505	1.618	-0.095	-0.087	
Female	6	-0.288	2.182	-0.172	2.117			-0.109	0.059
	7	-0.250	2.158	-0.135	2.132			-0.104	-0.030
	8	-0.276	2.295	-0.176	2.362	-0.283	2.990	-0.103	-0.066
	9	-0.294	2.330	-0.200	2.452	0.025	2.062	-0.097	-0.104
	10	-0.344	2.507	-0.230	2.571	0.051	2.028	-0.120	-0.043
	11	-0.308	2.460	-0.204	2.526	0.078	2.006	-0.089	-0.105
	12	-0.219	2.312	-0.107	2.342	0.225	1.804	-0.115	-0.021
	13	-0.117	2.196	-0.042	2.294	0.418	1.504	-0.051	-0.148
	14	0.041	1.920	0.105	2.021	0.574	1.257	-0.063	-0.103
15	0.203	1.662	0.253	1.787	0.599	1.281	-0.043	-0.139	

Source: Reference 2 (Tables 4 and 5)

## 10.5 Threshold Analysis Criteria

**Table 10-7 Threshold Criteria for Laboratory Tests**

Parameter	Criteria	Comments
Clinical Chemistry		
CPK	>ULN - $\leq 2.5 \times$ ULN >2.5 - $\leq 5 \times$ ULN >5 - $\leq 10 \times$ ULN >10 x ULN	CTCAE grades 1-4
Creatinine	>ULN - $\leq 1.5 \times$ ULN >1.5 - $\leq 3.0 \times$ ULN >3.0 - $\leq 6.0 \times$ ULN >6.0 x ULN	CTCAE grades 1-4
Blood Urea Nitrogen	>ULN - $\leq 1.5 \times$ ULN >1.5 - $\leq 3.0 \times$ ULN >3.0 - $\leq 6.0 \times$ ULN >6.0 x ULN	Same criteria as creatinine  No CTCAE
Sodium	Hyponatremia <LLN - $\geq 130$ mmol/L <130 - $\geq 120$ mmol/L <120 mmol/L  Hypernatremia >ULN - $\leq 150$ mmol/L >150 mmol/L - $\leq 155$ mmol/L >155 mmol/L - $\leq 160$ mmol/L >160 mmol/L	CTCAE grade 1, 3, 4  (No CTCAE grade 2)  CTCAE grade 1-4
Potassium	Hypokalemia <LLN - $\geq 3.0$ mmol/L <3.0 - $\geq 2.5$ mmol/L <2.5 mmol/L  Hyperkalemia >ULN - $\leq 5.5$ mmol/L >5.5 - $\leq 6.0$ mmol/L >6.0 - $\leq 7.0$ mmol/L >7.0 mmol/L	CTCAE grade 1&2, 3, 4  (Grade 1 and 2 are the same)  CTCAE grade 1-4
Total Cholesterol	>ULN - $\leq 7.75$ mmol/L >7.75 - $\leq 10.34$ mmol/L >10.34 - $\leq 12.92$ mmol/L >12.92 mmol/L	CTCAE grade 1-4
Triglycerides	>1.71 - $\leq 3.42$ mmol/L >3.42 - $\leq 5.7$ mmol/L >5.7 - $\leq 11.4$ mmol/L >11.4 mmol/L	CTCAE grade 1-4
Glucose	Hypoglycemia <3.0 - $\geq 2.2$ mmol/L <2.2 - $\geq 1.7$ mmol/L <1.7 mmol/L  Hyperglycemia >ULN - $\leq 8.9$ mmol/L >8.9 - $\leq 13.9$ mmol/L >13.9 - $\leq 27.8$ mmol/L >27.8 mmol/L	CTCAE grade 1-4  CTCAE grade 1-4

Albumin	<35 - ≥ 30 g/L <30 - ≥ 20 g/L <20 g/L	CTCAE grade 1-3
Amylase	>ULN - ≤ 1.5 x ULN >1.5 - ≤ 2.0 x ULN >2.0 - ≤ 5.0 x ULN >5.0 x ULN	CTCAE grade 1-4
Lipase	>ULN - ≤ 1.5 x ULN >1.5 - ≤ 2.0 x ULN >2.0 - ≤ 5.0 x ULN >5.0 x ULN	CTCAE grade 1-4
Direct bilirubin	>ULN - ≤ 1.5 x ULN >1.5 - ≤ 2 x ULN >2 - ≤ 3 x ULN >3 - ≤ 10 x ULN >10 x ULN	Same Criteria as Total Bilirubin  No CTCAE Not in DILI Guidance
GGT	>ULN - ≤ 2.5 x ULN >2.5 - ≤ 5.0 x ULN >5.0 - ≤ 20.0 x ULN >20.0 x ULN	CTCAE grade 1-4
Calcium	Hypercalcemia >ULN - ≤ 2.9 mmol/L >2.9 - ≤ 3.1 mmol/L >3.1 - ≤ 3.4 mmol/L >3.4 mmol/L	CTCAE grade 1-4
	Hypocalcemia <LLN - ≥ 2.0 mmol/L <2.0 - ≥ 1.75 mmol/L <1.75 - ≥ 1.5 mmol/L <1.5 mmol/L	CTCAE grade 1-4
Magnesium	Hypermagnesemia >ULN - ≤ 1.23 mmol/L >1.23 - ≤ 3.30 mmol/L >3.30 mmol/L	CTCAE grade 1, 3, 4  No CTCAE grade 2
	Hypomagnesemia <LLN - ≥ 0.5 mmol/L <0.5 - ≥ 0.4 mmol/L <0.4 - ≥ 0.3 mmol/L <0.3 mmol/L	CTCAE grade 1-4
Inorganic phosphate	Hypophosphatemia <0.74 - ≥ 0.6 mmol/L <0.6 - ≥ 0.3 mmol/L <0.3 mmol/L	CTCAE grade 1-4
ALT	>ULN - ≤ 3 xULN >3 - ≤ 5 xULN >5 - ≤ 8 xULN >8 - ≤ 20.0 xULN >20.0 x ULN	Per FDA DILI Guidance Jul 2009 and CTCAE
AST	>ULN - ≤ 3 xULN >3 - ≤ 5 xULN >5 - ≤ 8 xULN >8 - ≤ 20.0 xULN >20.0 x ULN	FDA DILI Guidance and CTCAE

ALT or AST	(ALT>ULN and ALT ≤ 3 xULN) or (AST>ULN and AST ≤ 3 xULN) (ALT>3 xULN and ALT ≤ 5 xULN) or (AST>3xULN and AST ≤ 5 xULN) (ALT>5 xULN and ALT ≤ 8 xULN) or (AST>5xULN and AST ≤ 8 xULN) (ALT>8 xULN and ALT ≤ 20 xULN) or (AST>8xULN and AST ≤ 20 xULN) ALT>20 xULN or AST> 20 xULN	FDA DILI Guidance
Alkaline Phosphatase	>ULN - ≤ 1.5xULN >1.5 - ≤ 2.5 xULN >2.5 - ≤ 5.0 x ULN >5.0 - ≤ 20.0 x ULN >20.0 x ULN	FDA DILI Guidance and CTCAE
Total Bilirubin	>ULN - ≤ 1.5 x ULN >1.5 - ≤ 2 x ULN >2 - ≤ 3 x ULN >3 - ≤ 10 x ULN >10 x ULN	FDA DILI Guidance and CTCAE
ALT and Total Bilirubin	ALT>3xULN and TBILI>2xULN	FDA DILI Guidance Jul 2009
AST and Total Bilirubin	AST>3xULN and TBILI>2xULN	FDA DILI Guidance Jul 2009
(ALT or AST) and Total Bilirubin	(ALT>3xULN or AST>3xULN) and TBILI>2xULN	FDA DILI Guidance Jul 2009
Hematology		
WBC	WBC decreased <LLN - ≥ 3.0 x 10e9 /L <3.0 - ≥ 2.0 x 10e9 /L <2.0 - ≥ 1.0 x 10e9 /L <1.0 x 10e9 /L	CTCAE grade 1-4
	Leukocytosis >100 x 10e9 /L	CTCAE grade 3 (only Grade available)
Lymphocytes	Lymphocyte decreased <LLN - ≥ 0.8 x10e9 /L <0.8 - ≥ 0.5 x10e9 /L <0.5 - ≥ 0.2 x10e9 /L <0.2 x10e9 /L	CTCAE grade 1-4
	Lymphocyte increased >4 - ≤ 20 x10e9/L >20 x10e9/L	CTCAE grade 2, 3 (only Grades available)
Neutrophils	Neutrophil decreased <LLN - ≥ 1.5 x10e9 /L <1.5 - ≥ 1.0 x10e9 /L <1.0 - ≥ 0.5 x10e9 /L <0.5 x10e9 /L	CTCAE grade 1-4
Hemoglobin	Hgb decreased (anemia) <LLN - ≥ 100 g/L <100 - ≥ 80 g/L < 80 g/L	CTCAE grade 1-3
	Hgb increased >ULN - ≤ 20 g/L above ULN >20 g/L above ULN - ≤ 40 g/L above ULN >40 g/L above ULN	CTCAE grade 1-3
Platelets	Platelet decreased <LLN - ≥ 75.0 x 10e9 /L	CTCAE grade 1-4

---

<75.0 – ≥ 50.0 x 10e9 /L  
<50.0 – ≥ 25.0 x 10e9 /L  
<25.0 x 10e9 /L

---

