#### **8.4.2 Clinical Laboratory Values**

For treatment-emergent laboratory measurements, the raw values and change from period baseline values for the continuous hematology, chemistry and coagulation results will be summarized in SI units by treatment group at each scheduled time point. For hematology, coagulation and chemistry measurements, the number and percentage of subjects with an abnormal low (<LLN) value and an abnormal high (>ULN) value at each analysis visit will be summarized.

The number and percentage of subjects with hematology, chemistry and coagulation values meeting the defined threshold criteria during the visit window for analysis visits will be summarized by analysis visit. Similarly, the hematology, chemistry and coagulation values meeting the defined threshold criteria during the overall TE period will be presented. The threshold analysis criteria are provided in Section 10.5 (Table 10-7 and Table 10-8).

For all LFT results (alanine aminotransferase [ALT], aspartate aminotransferase [AST], alkaline phosphatase [ALP], direct bilirubin, total bilirubin, and gamma-glutamyl transferase [GGT]), the following additional analyses will be conducted:

- A listing of subjects with elevated LFT results during the TE period will be presented. For each subject in the listing, LFT assessments at all visits during the TE period with elevated LFT will be included.
- For each of the LFTs, mean values ( $\pm$ SD) will be plotted by visit.
- The incidence of LFTs meeting threshold analysis criteria during the TE period against the period baseline threshold criteria will be summarized by treatment group (only worsening of the shift from period baseline will be presented).
- A scatter plot of the maximum ALT value across visits versus the maximum total bilirubin value also will be presented. The ALT and Total bilirubin values will be presented on a logarithmic scale. The graph will be divided into 4 quadrants with a vertical line corresponding to 3xULN for ALT and a horizontal line corresponding to 2xULN for total bilirubin. A similar graph of maximum AST value versus maximum total bilirubin value will be presented as well.

A summary table for the shift from period baseline to the value at Week 8 will be presented by treatment group for vitamin levels and lipid panel. A box plot of vitamin levels and lipid panel will also be plotted against visit.

For amylase and lipase, mean values ( $\pm$ SD) will be plotted by visit.

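### SAP Table 10-7 labels the low-glucose and low-phosphate rows as four CTCAE grades but prints three bands in each, so label and bands cannot both be right

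*SAP*

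**What the plan says.** SAP 10.5, Table 10-7, sets the bands for the laboratory threshold analysis. A comments column says which CTCAE grades each row represents.

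- Low glucose: "Hypoglycemia <3.0 - $\geq 2.2$ mmol/L <2.2 - $\geq 1.7$ mmol/L <1.7 mmol/L"
- Low inorganic phosphate: "Hypophosphatemia <0.74 - ≥ 0.6 mmol/L <0.6 - ≥ 0.3 mmol/L <0.3 mmol/L"

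The comment against each of these is "CTCAE grade 1-4".

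Elsewhere in the table, a row with fewer than four bands has a comment that says so. Hypokalaemia has three bands and the note "Grade 1 and 2 are the same". Hyponatraemia and hypermagnesaemia have three bands and the note "No CTCAE grade 2". Low calcium, labelled grades 1 to 4, has four bands and begins at the LLN: "Hypocalcemia <LLN - ≥ 2.0 mmol/L <2.0 - ≥ 1.75 mmol/L <1.75 - ≥ 1.5 mmol/L <1.5 mmol/L".

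SAP 8.4.2 puts the criteria to direct use. It summarises "The number and percentage of subjects with hematology, chemistry and coagulation values meeting the defined threshold criteria" by analysis visit, and presents the same criteria over the whole treatment-emergent period. The same section counts subjects below LLN and above the upper limit of normal at each analysis visit. It also lists individual chemistry results outside the reference range, from scheduled and unscheduled visits.

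**The concern.** Four labelled grades need four bands unless a note explains otherwise, and these two rows have neither. Either a band has been left out or the comment is wrong.

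The ambiguity has two practical effects. First, a reader or programmer cannot tell which grade the first printed band stands for. A phosphate of 0.65 mmol/L falls in that band. It would be the second of four grades if the mildest band is missing, the first of three if the label should be shorter, or a merged first and second grade if the row follows the hypokalaemia pattern.

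Second, both rows start at a fixed value rather than at the LLN. A result below the LLN but at or above the first cut would meet no criterion and would not be counted in either threshold table.

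**Working it through.** **Inputs.** Bands and comments come from SAP Tables 10-7 and 10-8, and the use of the criteria from SAP 8.4.2. The documents give no LLN for glucose or phosphate and do not reproduce the CTCAE cut-offs.

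**Step 1: bands against labels.** Tables 10-7 and 10-8 contain 29 rows or sub-rows whose comment refers to CTCAE grades alone. Of these, 19 are labelled grades 1 to 4:

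- High side (11), each with four bands: CPK, creatinine, sodium, potassium, total cholesterol, triglycerides, glucose, amylase, lipase, GGT, calcium.
- Low side (8): calcium, magnesium, WBC, lymphocytes, neutrophils and platelets, each with four bands; glucose and phosphate, each with three.

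So 11 + 6 = 17 of 19 match, and 19 − 17 = 2 do not. In the other 29 − 19 = 10 rows the comment agrees with the number of bands.

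**Step 2: where a missing band could lie.** The glucose bands run from below 3.0 to 2.2, from below 2.2 to 1.7, and then below 1.7 mmol/L with no lower bound. The phosphate bands run from below 0.74 to 0.6, from below 0.6 to 0.3, and then below 0.3 mmol/L with no lower bound. Neither set has an internal gap and both end in an open worst band. A missing band can therefore only lie at the mild end, above 3.0 or 0.74 mmol/L. The other six low-side rows labelled 1 to 4 all start at the LLN, which fits that reading but does not prove it.

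**Step 3: width of the uncovered interval.** Width = max(0, LLN − first cut). Every LLN below is an assumption.

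| Analyte | First cut (mmol/L) | Assumed LLN (mmol/L) | Uncovered width (mmol/L) |
|---|---|---|---|
| Glucose | 3.0 | 3.0 | 0 |
| Glucose | 3.0 | 3.3 | 3.3 − 3.0 = 0.3 |
| Glucose | 3.0 | 3.6 | 3.6 − 3.0 = 0.6 |
| Glucose | 3.0 | 3.9 | 3.9 − 3.0 = 0.9 |
| Glucose | 3.0 | 4.1 | 4.1 − 3.0 = 1.1 |
| Phosphate | 0.74 | 0.74 or lower | 0 |
| Phosphate | 0.74 | 0.80 | 0.80 − 0.74 = 0.06 |
| Phosphate | 0.74 | 0.87 | 0.87 − 0.74 = 0.13 |
| Phosphate | 0.74 | 0.97 | 0.97 − 0.74 = 0.23 |

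**Step 4: where an uncovered value would still be seen.** Under SAP 8.4.2:

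- by-visit count below LLN: included, without a grade;
- out-of-range listing: included;
- by-visit threshold table: absent;
- overall treatment-emergent threshold table: absent.

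The threshold shift summary in 8.4.2 is specified for liver function tests only. No other summary in that section gives an overall treatment-emergent count of low glucose or low phosphate.

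**The case against.** The strongest reply is that this is a labelling slip in an appendix and no more. The CTCAE text is not in the documents. A wrong comment, or two grades merged without a note, would look exactly like a missing band. A fixed first cut is not itself an omission: albumin starts at 35 g/L and triglycerides at 1.71 mmol/L, and both rows match their labels. If the laboratory LLN equals the first cut, nothing is lost. Protocol 12.3.4.2 describes these tables as counts of potentially clinically significant events and leaves criteria and parameter selection to the SAP. Several chemistry analytes in Protocol Table 11-1, chloride and bicarbonate among them, have no Table 10-7 row, so full coverage of abnormal values was never promised. Safety analysis is descriptive (SAP 8.4), and clinically significant laboratory abnormalities are reported as adverse events in any case (Protocol 11.7.2).

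Most of this stands, and it limits the consequence. It does not remove the contradiction between four labelled grades and three bands, which holds whatever the LLN is. Loss of a line in the PDF conversion cannot be wholly excluded, but it is unlikely: neighbouring multi-band cells are intact and both rows fail in the same way.

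Two stronger readings are tempting. A reader might infer that the lowest CTCAE grade is definitely never tabulated; without the CTCAE cut-offs the documents cannot show that. A reader might also infer that most below-normal results vanish from the safety output. Any such share would need an assumed distribution and an assumed LLN, and its range starts at zero. Values that miss the threshold tables remain in the by-visit counts and the listing.

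**Conclusion.** The inconsistency is real and confined to two of the 19 rows or sub-rows labelled grades 1 to 4. A missing mildest band is the likelier explanation, given how the other low-side rows are built, but a wrong comment remains possible.

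The loss of mild low values from the threshold tables is conditional: it occurs only if the laboratory LLN exceeds 3.0 mmol/L for glucose or 0.74 mmol/L for phosphate. Where it occurs, what goes missing is the grade and the overall treatment-emergent count of mild lows, not the results themselves. Efficacy, sample size and type I error are unaffected. This is a minor correction, worth making because the table is a working programming rule that contradicts itself.

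**What to change.** Reconcile bands and comments for both rows before database lock, in one of two ways.

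1. Add a mildest band from below the LLN down to the present first cut (3.0 mmol/L for glucose, 0.74 mmol/L for phosphate), as in the other low-side rows labelled grades 1 to 4. Check it first against the CTCAE version used. Table 10-7 names no version; Protocol 13.1.1.4 cites version 4.0, but for adverse-event severity.
2. If three bands were intended, correct the comment to the grades actually shown, with a note like those for potassium and sodium, and add an overall treatment-emergent count of subjects below LLN for both analytes.

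The cost is two table rows in the SAP and the matching program format, plus one extra count under the second option. The downside is slightly longer tables with more mild events in them.

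### The combined ALT-or-AST bands in SAP Table 10-7 overlap, so a subject with discordant enzymes counts in two bands and the bands cannot be added

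*SAP*

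**What the plan says.** SAP Table 10-7 (Section 10.5) bands ALT and AST separately, each at >1 to ≤3, >3 to ≤5, >5 to ≤8, >8 to ≤20 and >20 x ULN. It then adds a combined ALT-or-AST parameter with the same cut-offs:

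- Band 1: "ALT>ULN and ALT ≤ 3 xULN) or (AST>ULN and AST ≤ 3 xULN"
- Band 2: "ALT>3 xULN and ALT ≤ 5 xULN) or (AST>3xULN and AST ≤ 5 xULN"
- Band 3: "ALT>5 xULN and ALT ≤ 8 xULN) or (AST>5xULN and AST ≤ 8 xULN"
- Band 4: "ALT>8 xULN and ALT ≤ 20 xULN) or (AST>8xULN and AST ≤ 20 xULN"
- Band 5: "ALT>20 xULN or AST> 20 xULN"

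SAP Section 8.4.2 uses the criteria in two summaries of numbers of subjects. By visit, it counts "values meeting the defined threshold criteria during the visit window for analysis visits will be summarized by analysis visit". Over the whole treatment-emergent period, "values meeting the defined threshold criteria during the overall TE period will be presented". Neither statement says that a subject is counted only in the worst band, or that a subject may appear in several.

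Section 8.4.2 also plans a shift summary: "The incidence of LFTs meeting threshold analysis criteria during the TE period against the period baseline threshold criteria will be summarized by treatment group", limited to worsening. That item sits under a list of six single analytes (ALT, AST, ALP, direct bilirubin, total bilirubin and GGT). The combined parameter is not on the list.

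**The concern.** Bands with both a lower and an upper limit look like exclusive severity categories. For one enzyme in one sample they are. For the combined row they are not, because the two halves of each criterion are joined by *or* with no condition on the other enzyme. A subject whose enzymes lie in different elevated bands is therefore counted twice, once in the band of the higher enzyme and once in a milder one.

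The combined row is the only threshold row that could give the number of subjects with either transaminase above a limit regardless of bilirubin. Separate ALT and AST counts cannot be added, because the same subject may be in both. Protocol Section 11.7.7 frames liver monitoring on ALT or AST at 3, 5 and 8 x ULN, so counts above those limits are ones that a reader of the liver tables will want. As printed, they cannot be got by adding bands.

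**Working it through.** **Inputs.** The five combined criteria in SAP Table 10-7 and the counting rules in SAP Section 8.4.2. The plan states no figure on this point, so there is none to reproduce.

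**Step 1: apply the criteria as printed to one sample.** Each enzyme is either not elevated (0) or in one of bands 1 to 5, which gives 6 x 6 = 36 pairs.

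| Type of pair | Number of pairs | Bands met |
|---|---|---|
| Neither elevated | 1 | 0 |
| Only one elevated | 2 x 5 = 10 | 1 |
| Both in the same elevated band | 5 | 1 |
| Both elevated, different bands | 5 x 4 = 20 | 2 |

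So 20 pairs meet two bands, 15 meet one and 1 meets none.

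**Step 2: compare with banding on the maximum.** As printed, band *k* is met by every pair in which at least one enzyme is in *k*: 36 − 5 x 5 = 11. Banded on the higher enzyme, band *k* holds 2*k* + 1 pairs.

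| Band (x ULN) | As printed | On the maximum |
|---|---|---|
| >1 to ≤3 | 11 | 3 |
| >3 to ≤5 | 11 | 5 |
| >5 to ≤8 | 11 | 7 |
| >8 to ≤20 | 11 | 9 |
| >20 | 11 | 11 |
| Total | 55 | 35 |

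The printed total is 15 + 2 x 20 = 55 for 35 elevated pairs. In all 35, the highest band met equals the band of the maximum. The error therefore runs one way: bands 1 to 4 can gain subjects whose peak is higher, and band 5 is unaffected.

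**Step 3: add bands to get counts above a limit.**

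| Limit (x ULN) | Sum of printed bands | Pairs truly above | Excess |
|---|---|---|---|
| >3 | 44 | 5 + 7 + 9 + 11 = 32 | 12 |
| >5 | 33 | 7 + 9 + 11 = 27 | 6 |
| >8 | 22 | 9 + 11 = 20 | 2 |
| >20 | 11 | 11 | 0 |

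The excess comes only from pairs with both enzymes above the limit but in different bands. For example, ALT 6 and AST 4 x ULN counts twice above 3. ALT 9 and AST 2 x ULN counts once above 3; its second entry goes to the mildest band.

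These are counts of logical combinations, not patient frequencies. A single sample meets at most two bands, so with one sample per subject the summed count lies between the true number and twice that number. The documents do not say where in that range.

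**Step 4: several visits.** Over the treatment-emergent period, one enzyme alone can meet several bands: ALT at 2, 6 and 4 x ULN on three visits meets bands 1, 3 and 2. That gap affects every banded laboratory row. The combined row differs in that it overlaps within one sample, so its by-visit table is affected too.

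**The case against.** The best defence is that Section 8.4.2 plans a count per criterion. It does not say that the bands are exclusive, that they sum, or that they show each subject's peak. Overlapping criteria are common in the same appendix: Table 10-9 lists heart rate >100, >115 and >130 bpm together, and several nested QTc increases. This stands in part: the table is not wrong as a count of any occurrence. But those nested criteria are open-ended, so their overlap is plain and each line is itself a count above a limit. The combined liver bands have upper limits, and nothing tells the reader that they overlap.

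A reader might infer that the table misstates peak transaminase severity. It does not. The highest band met is always correct, and peak values appear elsewhere: separate ALT and AST bands, a listing of elevated liver tests, and plots of each subject's maximum ALT and AST against maximum bilirubin. Counts above a limit could be rebuilt from the data, though not from the banded rows.

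A reader might also infer that the shift table uses the combined bands, so that a discordant subject has two baseline categories. The SAP does not say so; it names only single analytes there. The question arises only if the combined parameter is added.

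Finally, Protocol Section 11.7.7 governs individual subjects from their own results and does not depend on this table, and SAP Section 8.4 plans no safety testing. Both points stand.

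**Conclusion.** The combined bands overlap as printed, and no counting rule resolves it. The lower bands can include subjects whose peak is higher, and the numbers above 3, 5 and 8 x ULN cannot be obtained by adding bands. The highest band met, and the count above 20 x ULN, are correct.

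This is a minor but real specification fault in a descriptive safety table. Efficacy inference, data collection and subject management are untouched. The numerical effect is probably small, but the number of discordant cases cannot be derived from the documents. The logical result rests only on the criteria as printed. Table shells were not available and might settle the display.

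**What to change.** 1. In Table 10-7, define the combined row on the higher of ALT/ULN and AST/ULN: >1 to ≤3, >3 to ≤5, >5 to ≤8, >8 to ≤20, >20. Each elevated sample then falls in exactly one band.
2. In Section 8.4.2, state that each subject is counted once, at the worst value in the visit window or treatment-emergent period. For the by-visit table, say how this fits the Section 8.1 rule that takes the safety record closest to the target day. With steps 1 and 2, the bands add up to the number of subjects above each limit.
3. State whether the combined parameter enters the shift table. If it does, apply the same maximum rule at period baseline.

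The cost is one derived variable and a few sentences before database lock, with no new data.
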